12.4 Data collected at the Observational visit (V2) and Final Visit (V3)

Data to be collected directly on Observational visit (V2) and Final visit (V3):

- Date of visit (day, month, year)
- Type of visit: visit to physician office or distant contact
- Physical examination: weight (kg), body mass index calculation;
- IBD assessment at the time of the visit:
 - Disease extent according to the following Montreal Classification categories;
- Disease activity data at the visit will consist of specified signs and symptoms depending on the disease type:
 - CD: abdominal pain severity, number of liquid stools per day, presence of an abdominal mass, endoscopic findings (if done), documented presence of CD complications, and Harvey Bradshaw Index or other documented disease activity scales (if applicable).
 - UC: frequency of stools/day, rectal bleeding, endoscopic findings (if done), physician global assessment of disease severity, and Mayo scores or other documented disease activity scales (if applicable).
- IBD status (with current/last available data by the date of the visit):

- IBD status as judged by investigator (remission, incomplete remission, flare, others), nature of remission at the time of examination;
- IBD flare(s);
- Systemic (extra intestinal) IBD manifestations;
- IBD complications;
- Vaccination in accordance with IBD treatment guidelines.
- Laboratory and instrumental evaluation of IBD (if done within routine practice) - for details please section 12.8;
- IBD treatment;
- IBD surgical treatment;
- Healthcare resources utilization;
- Concomitant treatment
- Adverse events and adverse drug reactions (seriousness, severity, causality, start and stop dates, action, frequency, outcomes):
 - adverse drug reactions on IBD treatments,
 - adverse events on Entivyo® (Vedolizumab) treatment,
 - serious adverse events on IBD treatments (including Entivyo® (Vedolizumab) treatment).

All adverse events and adverse drug reactions must be documented on the Adverse Report Form which is appended to the Case Report Form.

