13.2.3. Collection and reporting of AEs and ADRs

The following safety data should be reported by the investigator to the responsible CRO:

- adverse drug reactions on IBD treatments,
- adverse events on Entivyo® (vedolizimab) treatment,
- serious adverse events on IBD treatments (including Entivyo® (vedolizumab) treatment).

Start of AEs and ADRs collection: AEs/ADRs must be collected from the date after ICF signing. Routine collection of AEs/ADRs will continue until Final visit (Visit 3).

A physician must report all reportable AEs and ARDs on the special “AE reporting form” provided by the Sponsor. The physician should record only one AE per 1 “AE reporting form”. The physician has to record the diagnosis if available. If no diagnosis is available, the physician should record each sign and symptom as separate reports.

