## 7.2 ***Methods and timelines for the assessment of safety endpoints***

Start of AEs and ADRs collection: AEs/ADRs must be collected from the date after ICF signing. Routine collection of AEs/ADRs will continue until Final visit (Visit 3).

A physician must report all reportable AEs and ARDs on the special “AE reporting form” provided by the Sponsor. The physician should record only one AE per 1 “AE reporting form”. The physician has to record the diagnosis if available. If no diagnosis is available, the physician should record each sign and symptom as separate reports

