#### 8.1.4 Data tabulation principles

All data will be presented descriptively for each defined treatment pattern and can be further divided into subgroups depending on the presence of certain factors of interest in data (see section 7.4).

All summary tables will be structured with a column for each pattern in the defined order and will be annotated with the total population size relevant to that pattern, including any missing observations relevant for the particular table.

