#### 8.1.5 Safety data analysis

Collection of safety data starts with the signing of ICF for this study, so, there will be no safety data available for the retrospective part of the study.

Protocol ID	MACS-2017-102279	STATISTICAL ANALYSIS PLAN	Page 27 of 41	
IP	N/A		Date	30.12.2021
ID	MACS-2017-102279_SAP		Version	v1.2 final

Safety data will be presented for the population of all patients enrolled as well as for each defined treatment combination (or pattern, if applicable) separately. Data will be presented as total counts as well as distribution by SOC at Visits 1, 2 and 3:

- Overall frequency of all AEs;
- Frequency of all AEs that led to treatment discontinuation / treatment change regardless of their relation to a particular medication;
- Frequency of SAEs;
- Frequency of all SAEs that led to treatment discontinuation / treatment change regardless of their relation to a particular medication;
- Frequency of ADRs;
- Frequency of SADRs;
- Frequency of pregnancy cases.

Additionally, all AEs/SAEs and ADRs/SADRs will be tabulated according to their relation to a particular medication (see example Table 17), separate tables will be generated for each medication being a monotherapy and in treatment combination.

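### The documents do not settle whether non-serious, unrelated AEs are collected off vedolizumab, so the all-AE outputs of SAP 8.1.5 may not be comparable across treatments

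*SAP*

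**What the plan says.** **Collection, narrow wording.** Protocol 13.2.3 names three classes for the investigator to report: ADRs on IBD treatments, "adverse events on Entivyo® (vedolizimab) treatment", and SAEs on IBD treatments. Protocol 12.4 has the same list, with "adverse events on Entivyo® (Vedolizumab) treatment" as the only item for AEs as such, and SAP 5.3.2 and 5.3.3 repeat it. SAP 7.2, like protocol 13.2.3, adds a limiting word: "A physician must report all reportable AEs and ARDs". The outputs planned in SAP 8.7 for the 2020 interim use the same three-way split, although a footnote there says that analysis was not performed.

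**Collection, broad wording.** Directly after the list, protocol 12.4 and SAP 5.3.2 state: "All adverse events and adverse drug reactions must be documented on the Adverse Report Form". Protocol 13.2.2 says that AEs and ADRs without exception go on the eCRF page for AEs. The table in protocol 12.8 sends any medical event after consent to Adverse Events.

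**Analysis.** SAP 8.1.5 presents safety for all enrolled patients and for each treatment combination or pattern. Its rows include "Overall frequency of all AEs" and "Frequency of all AEs that led to treatment discontinuation / treatment change regardless of their relation to a particular medication". On format it says: "Data will be presented as total counts as well as distribution by SOC at Visits 1, 2 and 3". It adds tables of AEs and ADRs by relation to each medication. SAP 8.1.4 sets the layout: "All summary tables will be structured with a column for each pattern in the defined order". Protocol 15.2.3 also summarises all AEs, by body system.

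**The concern.** If AEs as such are collected only on vedolizumab, a non-serious event judged unrelated enters the database for a patient on vedolizumab and not for a patient on another therapy. An all-AE row set side by side by treatment would then compare different collection rules as well as different drugs. A reader could take a difference in ascertainment for a difference in safety.

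Reading across drugs is foreseeable. SAP 4.2 adds an exploratory objective on safety in patient subgroups, SAP 7.4 defines first-line subgroups for vedolizumab, ustekinumab, anti-TNF and tofacitinib, and SAP 8.1.1 plans exploratory associations between treatment patterns and outcomes.

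**Working it through.** **1. Which event classes are in scope for a patient not on vedolizumab?**

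| Event class | Narrow lists | Broad wording |
|---|---|---|
| ADR | collected | collected |
| SAE | collected | collected |
| Non-serious, not related | not listed | collected |

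On vedolizumab all three classes are collected under either wording. Only the last line differs, and no section gives precedence. If everything were collected for everyone, the separate vedolizumab item would be redundant, and the limiting word in protocol 13.2.3 and SAP 7.2 also points to the lists. Neither observation settles the matter.

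**2. Which outputs need that class?** SAP 8.1.5 has seven rows. Two use it: all AEs, and all AEs leading to discontinuation or change. Four (SAEs, SAEs leading to discontinuation or change, ADRs, SADRs) have the same scope on every treatment. The lists do not cover the pregnancy row. The by-medication AE tables, the all-enrolled column and the protocol 15.2.3 summary inherit the mixed scope. The endpoints in SAP 7.1 are related ADRs and related SAEs, so they do not.

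**3. Size at patient level (illustration under the narrow lists).** The documents give no AE rates, so every input here is an assumption:

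- s = share of patients with any AE whose AEs are all non-serious and unrelated.
- a, b = probability that such a patient, in the vedolizumab column (a) or another column (b), has at least one such AE while on vedolizumab.

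With equal true any-AE risk, the risk cancels:

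ratio (vedolizumab column / other column) = [1 − s(1 − a)] / [1 − s(1 − b)]

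| s | a=1, b=0 (no switching) | a=0.8, b=0.1 | a=0.6, b=0.2 | a=0.2, b=0.4 |
|---|---|---|---|---|
| 5% | 1/0.95 = 1.05 | 0.99/0.955 = 1.04 | 0.98/0.96 = 1.02 | 0.96/0.97 = 0.99 |
| 20% | 1/0.80 = 1.25 | 0.96/0.82 = 1.17 | 0.92/0.84 = 1.10 | 0.84/0.88 = 0.95 |
| 40% | 1/0.60 = 1.67 | 0.92/0.64 = 1.44 | 0.84/0.68 = 1.24 | 0.68/0.76 = 0.89 |
| 60% | 1/0.40 = 2.50 | 0.88/0.46 = 1.91 | 0.76/0.52 = 1.46 | 0.52/0.64 = 0.81 |

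Protocol 13.1.5 counts an event as related whenever drug involvement cannot be excluded. That pulls s down, so the low rows deserve weight. The discontinuation row needs its own share, s_d. With no switching, 1/(1 − s_d) is 1.05, 1.11 and 1.25 at s_d = 5%, 10% and 20%.

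**4. Size for event counts.** SAP 8.1.5 also shows total counts. If r is the assumed share of events that are related or serious, the no-switching count ratio is 1/r: 1.25, 1.67, 2.5 and 5.0 at r = 0.8, 0.6, 0.4 and 0.2.

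**5. Direction.** The ratio exceeds 1 only if a > b, that is, if the vedolizumab columns carry more vedolizumab exposure during follow-up. SAP 8.1.3 fixes the so-called original combination at the start of the retrospective period, about two years before AE collection begins, and SAP 8.1.2 lets patterns change over time. Under that definition the gap between a and b may narrow or, less likely, reverse, as in the last column of the table.

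**The case against.** The strongest reply is that the harm is conditional. If the broad wording was followed at every site, capture is uniform and the ratio is 1. The affected outputs are descriptive, the formal endpoints have uniform scope, the stated safety split is biologic against non-biologic and by prior biologic use, and protocol 15.2.4 already acknowledges the limits of uncontrolled data. All of this stands, and it holds the severity down. It does not say which rule sites followed. The word *all* may only mean all events just listed, but that reading would make the narrow lists govern, which is the case that damages comparability.

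The by-medication tables in SAP 8.1.5 help in part, because they show related events separately. Their AE counts still carry the mixed scope. The example tables in SAP section 9 were not available for this review, so it cannot be said that no scope footnote exists anywhere.

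A reader might go further and infer that the plan biases safety against vedolizumab. The documents do not support that: the collection rule is unsettled, the direction depends on exposure during follow-up, and the ADR, SAE and SADR rows are unaffected. Nor would finding some non-serious unrelated AEs recorded off vedolizumab prove full capture, since some entries do not show completeness. Finding none would not separate non-collection from non-occurrence.

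**Conclusion.** The point holds conditionally, at minor to moderate severity. The scope of AE collection is contradictory and no section resolves it. If the narrow lists govern, or if sites applied the two wordings unevenly, the two all-AE rows, the by-medication AE tables and the protocol 15.2.3 summary are not comparable across treatments, and the all-enrolled column mixes two scopes.

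Under the lists, the rows run upward for vedolizumab when its columns hold more vedolizumab exposure during follow-up than the others. The size is not derivable from the documents: nil under uniform full capture, small if few patients have only non-serious unrelated events, and larger only at the higher assumed shares with little switching.

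**What to change.** 1. Reconcile protocol 12.4, 12.8, 13.2.2 and 13.2.3 with SAP 5.3.2, 5.3.3 and 7.2. Establish from the eCRF completion instructions and site training which rule sites were given. Protocol 10.2 planned data collection to end in Q3–Q4 2021 and SAP v1.2 is dated 30.12.2021, so this probably documents what was captured and cannot change it.
2. Cross-tabulate IBD medication, causality and seriousness by site, all of which are on the AE form (protocol 13.2.2). Use this as a screen for uneven capture only.
3. If one uniform all-AE rule is documented, keep the rows and state the rule in a footnote.
4. Otherwise, limit comparisons across treatments to ADRs and SAEs. Show all AEs, and all AEs leading to discontinuation or change, only for events with onset during vedolizumab exposure, labelled as such. Put the scope footnote on the all-enrolled column, the by-medication AE tables and the protocol 15.2.3 summary.
5. Report the change under SAP 8.5, with sponsor approval where it departs from the protocol.

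The cost is the reconciliation of seven sections, one cross-tabulation, footnotes and possibly two redefined rows. No new data are needed. The downside is that the cross-treatment all-AE comparison may be lost.

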#### 8.1.6 Listing generation principles

All data will be listed, sorted by site and patient, and when appropriate by visit number within patient. As described in ICH E3 guidelines, each listing will include patient's demographics (age and gender) for ease of reading and interpretation. Listings can be saved in Excel sheets.

### 8.2 Determination of sample size

The primary objective of this study is to obtain the accurate and comprehensive information regarding the treatment regimens used in patients with moderate to severe UC and CD flare within routine clinical practice in Russia, Belarus and Kazakhstan. For this purpose, sample size should be large enough to contain essential number of patients with different therapy options.

One of the key secondary objectives is to assess the percentage of Ulcerative Colitis (UC) and Crohn's Disease (CD) patients with at least one episode of failure of non-biological therapy with immunosuppressive agents or biological therapy registered within 12 months from the beginning of moderate to severe IBD flare. Based on literature data, up to 20-40% of IBD patients experience failure of TNF antagonist therapy initially, and in 10-20% of patients per year loss of response is observed.

Assuming the percent of patients receiving biological therapy in the study population is 40%, about 40% proportion of CD patients and that 40-50% of the patients on biological therapy will have at least one episode of treatment failure during 12 months, enrolment of 3000 patients totally will be sufficient to estimate the proportion of patients on biological therapy with treatment failure during the 12 months of observation with acceptable precision in both UC and CD subgroups ( $\pm 4.7\%$  for the smaller subgroup of CD patients and the assumed failure rate of 50%). The table below shows 95% confidence intervals for the estimated proportions of 40%,

Protocol ID	MACS-2017-102279	STATISTICAL ANALYSIS PLAN	Page 28 of 41	
IP	N/A		Date	30.12.2021
ID	MACS-2017-102279_SAP		Version	v1.2 final

50% and different sample size values. For other, more prevalent subgroups (CD patients on non-biological therapy, UC patients on each type of therapy) the proposed sample size will also allow to estimate proportion of patients with treatment failure with same or higher precision.

Table 2. Sample size and corresponding precision of estimate

The total number of patients to be enrolled	The number of CD patients on biotherapy*	The number of CD patients in the analysis assuming 10% drop-out	Assumed failure rate of biological therapy**	
			40%	50%
2000	320	288	34.3-45.7%	44.2-55.8%
2500	400	360	34.9-45.1%	44.8-55.2%
3000	480	432	35.4-44.6%	45.3-54.7%
3500	560	504	35.7-44.3%	45.6-54.4%
4000	640	576	36.0-44.0%	45.9-54.1%
4500	720	648	36.2-43.8%	46.2-53.8%
5000	800	720	36.4-43.6%	46.3-53.7%

\* Assuming the percent of patients receiving biotherapy is 40% among the study population. The precision (95% CI) is shown for the smaller subgroup of CD patients (approximately 40%).

\*\* 95% confidence intervals are shown.

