- To evaluate and describe the implementation and achievement of Treat-to-target (T2T) goals in real-world clinical practice in moderate to severe IBD patients treated by biological and non-biological therapy during 2 years before enrolment and 1 year observational period after enrolment by treatment type 1) to assess the extent to which proposed Treat to Target goals are achieved in moderate to severe UC/CD patients 2) to describe how and when UC/CD disease activity is assessed 3) to evaluate the potential challenges to achieving T2T targets during routine care ;

- Establish the impact on healthcare resources utilization for patients with moderate to severe UC and CD

Safety Objective:

- To describe the incidence of real-world safety data occurred during 12-months treatment period within routine clinical practice by treatment type (biologics or non-biological IBD therapy) and treatment history (biologic treatment naïve or with prior biological treatment).

Exploratory objective:

- To assess TB in moderate to severe IBD patients receiving biologics and/or non-biological treatment.

Methodology

Study Design: International, multicentre, non-interventional retrospective and prospective study.

Study plan: The definition of a Non-Interventional study is provided in Guidelines for Good Pharmacovigilance Practices (GVP) of Eurasian Economic Commission No. 87 [20]. During participation in the study patients are observed according to the local routine practice. The assignment of a particular therapeutic strategy to the patient including all diagnostic procedures is decided in accordance with Clinical recommendations of the Russian gastroenterological association and association of coloproctologists of Russia on the diagnosis and treatment of ulcerative colitis and Crohn's disease; Clinical Protocols of diagnosis and treatment of ulcerative colitis and Crohn's disease in the Republic of Kazakhstan and Clinical Protocol "Diagnosis and treatment of patients with diseases of the digestive system", Appendix 3 in the Republic of Belarus and local routine practice [6-10]..

Number of patients

Approximately 2000 patients will be enrolled in the study.

Diagnosis/Disease/Condition and main criteria for inclusion

Inclusion criteria:

1. Male and female patients 18 years or older by the time of enrolment
2. Confirmed diagnosis of Crohn's disease or ulcerative colitis for at least 2 years prior to enrolment in the study.

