10.5 Premature Termination or Suspension of Study or Investigational Site

The study will be completed as planned unless when temporary suspension or early termination required.

The Sponsor has the right to terminate the study providing a preliminary notification to investigators and hospitals. The Sponsor has the right to unilaterally stop enrolment of patients and data collection at any time in the study by providing a preliminary written notification to investigators and hospitals with date of stop of enrolment. The Sponsor should ensure that notification about premature termination or suspension of the study is submitted to the concerned authorities, IEC and LEC/IRB (if applicable).

The investigator has the right to stop recruitment at any time with serving a preliminary written notice to the Sponsor/responsible CRO.

In case of premature closure of the site/termination of the study, all documentation forms (except documentation that has to remain stored at site) must be returned to the Sponsor, even unused ones. Study material may be destroyed only with permission of the Sponsor.

11 The Study Population

The patients will be treated in accordance with local routine clinical practice. Patient eligibility is determined according to the following inclusion and exclusion criteria. Patients should be included in the study only once.

Approximately 2000 patients should be included into the study in accordance with the inclusion/exclusion criteria below.

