15.3 Interim Analyses

One interim data analysis is planned in this study – in 2019. The final statistical analysis will be performed after the end of the study and database lock.

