15.4 Determination of Sample Size

The primary objective of this study is to obtain the accurate and comprehensive information regarding the treatment regimens used in patients with moderate to severe UC and CD flare within routine clinical practice in Russia, Belarus and Kazakhstan. For this purpose, sample size should be large enough to contain essential number of patients with different therapy options.

One of the key secondary objectives is to assess the percentage of Ulcerative Colitis (UC) and Crohn's Disease (CD) patients with at least one episode of failure of non-biological therapy with immunosuppressive agents or biological therapy registered within 12 months from the beginning of moderate to severe IBD flare. Based on literature data, up to 20-40% of IBD patients

experience failure of TNF antagonist therapy initially, and in 10-20% of patients per year loss of response is observed.

Assuming the percent of patients receiving biological therapy in the study population is 40%, about 40% proportion of CD patients [5, 6] and that 40-50% of the patients on biological therapy will have at least one episode of treatment failure during 12 months, enrolment of 2000 patients totally will be sufficient to estimate the proportion of patients on biological therapy with treatment failure during the 12 months of observation with acceptable precision in both UC and CD subgroups ($\pm 5.8\%$ for the smaller subgroup of CD patients and the assumed failure rate of 50%). The table below shows 95% confidence intervals for the estimated proportions of 40%, 50% and different sample size values. For other, more prevalent subgroups (CD patients on non-biological therapy, UC patients on each type of therapy) the proposed sample size will also allow to estimate proportion of patients with treatment failure with same or higher precision.

The total number of patients to be enrolled	The number of CD patients on biotherapy*	The number of CD patients in the analysis assuming 10% drop-out	Assumed failure rate of biotherapy**	
			40%	50%
2000	320	288	34.3-45.7%	44.2-55.8%
2500	400	360	34.9-45.1%	44.8-55.2%
3000	480	432	35.4-44.6%	45.3-54.7%
3500	560	504	35.7-44.3%	45.6-54.4%
4000	640	576	36.0-44.0%	45.9-54.1%
4500	720	648	36.2-43.8%	46.2-53.8%
5000	800	720	36.4-43.6%	46.3-53.7%

* Assuming the percent of patients receiving biotherapy is 40% among the study population. The precision (95% CI) is shown for the smaller subgroup of CD patients (approximately 40%).

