[https://docs.eaeunion.org/docs/ru-ru/01427633/err\\_06112020\\_19](https://docs.eaeunion.org/docs/ru-ru/01427633/err_06112020_19). Accessed 30 December 2021.

Protocol ID	MACS-2017-102279	STATISTICAL ANALYSIS PLAN	Page 6 of 41	
IP	N/A		Date	30.12.2021
ID	MACS-2017-102279_SAP		Version	v1.2 final

- Non-interventional study protocol IBD-5005 (MACS-2017-102279) version 4.0 dated 28-Oct-2019.

The purpose of this statistical analysis plan is a more detailed, compared to the section 15 of the protocol, description of the main principles of statistical analysis conduct as planned per protocol, description of methods of primary and secondary endpoint analysis as well as other data collected during the study.

This plan assumes the full compliance of planned and conducted analyses to the study protocol, including the study population (data sets) definitions, any applicable data transformation or compensation, required number of subjects, etc. All discrepancies compared to the study protocol should be explained, and a rationale should be provided.

Protocol ID	MACS-2017-102279	STATISTICAL ANALYSIS PLAN	Page 7 of 41	
IP	N/A		Date	30.12.2021
ID	MACS-2017-102279_SAP		Version	v1.2 final

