### **8.7 Interim analysis**

Two interim analyses are planned – in 2019 and 2020 – with corresponding interim data locks for the completed cases:

- 2019: about 700 completed cases for retrospective data analysis
- 2020^2: 3000 completed cases for retrospective and partial prospective data (up to 6 months)

---

 According to the current version of the protocol, the set of collected data has been reduced to 2000 cases. Therefore, the second analysis (second look) of data was not performed in 2020.

Protocol ID	MACS-2017-102279	STATISTICAL ANALYSIS PLAN	Page 30 of 41	
IP	N/A		Date	30.12.2021
ID	MACS-2017-102279_SAP		Version	v1.2 final

All cases will be included into interim analysis with the prerequisite of complete data cleaning, i.e., corresponding eCRF forms are complete, free of any pending queries and signed by the corresponding investigator.

Retrospective data analysis (2019): will include the following endpoints (all endpoints will be assessed retrospectively for the period of 2 years of retrospective data collection):

- 1) Treatment patterns associated with prior biologic agents use or non- biological therapy according to the algorithm provided in the section 8.1.2);
- 2) Demographic data, medical history, treatment history, concurrent diseases, concomitant medications by treatment group/pattern;
- 3) Demographic data for FAS;
- 4) Family history of IBD, smoking habits, medical history comorbidities for FAS;
- 5) Disease characteristics: age of disease onset, location of disease, clinical course, disease severity, intestinal and systemic (extraintestinal) manifestations, complications in history for FAS;
- 6) Frequency and methods of assessment of UC/CD disease activity;
- 7) Assessment of healthcare resource utilization;
- 8) TB incidence and prevalence in IBD patients by treatment pattern;
- 9) TB medication's use in IBD patients by treatment pattern;
- 10) Compliance between the assessment of IBD status by investigator and objective methods of assessment (Mayo index, Harvey-Bradshaw index, instrumental assessments).

No safety analysis will be performed for the retrospective data analysis as there will be no safety data in the retrospective part of the study.

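### SAP section 8.2 still justifies 3000 patients and ±4.7% for CD patients on biologics, while the study size is now about 2000, which gives ±5.8%

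*SAP*

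**What the plan says.** SAP v1.2 (30.12.2021), section 8.2, says "enrolment of 3000 patients totally will be sufficient to estimate the proportion of patients on biological therapy with treatment failure". It gives the precision as ±4.7% for the smaller subgroup, CD patients on biologics, at an assumed failure rate of 50%. It then says that, for the other disease-by-therapy groups, "the proposed sample size will also allow to estimate proportion of patients with treatment failure with same or higher precision".

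Protocol section 15.4 has almost the same paragraph with different figures: "enrolment of 2000 patients totally will be sufficient to estimate the proportion of patients on biological therapy with treatment failure", with ±5.8% for the same group and rate. The protocol summary (section 2) says "Approximately 2000 patients will be enrolled in the study", and section 11 says "Approximately 2000 patients should be included into the study in accordance with the inclusion/exclusion criteria below".

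The SAP acknowledges the smaller study in one place, footnote 2 to section 8.7: "According to the current version of the protocol, the set of collected data has been reduced to 2000 cases". The footnote is attached to the 2020 interim look and explains why that look was not done.

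Section 3 of the SAP says the plan assumes full compliance with the protocol, and its list of what that covers includes "any applicable data transformation or compensation, required number of subjects, etc". It asks for any discrepancy to be explained with a rationale.

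**The concern.** One version of the SAP justifies 3000 patients in section 8.2 and accepts 2000 in section 8.7. Table 2 lists seven totals from 2000 to 5000, so only the sentence above it tells the reader which total was chosen, and it names the wrong one. Section 8.2 gives no reason for differing from the protocol, although section 3 asks for one.

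The study tests no hypothesis for its primary endpoint, so stated precision is the only quantitative argument for its size. A report that took its planned sample size from section 8.2 would give the wrong total and overstate the planned precision for CD patients on biologics.

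**Working it through.** **Inputs** (the same in SAP section 8.2 and protocol section 15.4): 40% of patients with CD; 40% on biologics; 10% drop-out; failure rate 40% to 50%, with the headline half-width at 50%; 95% confidence. Total enrolled: 3000 in the SAP, 2000 in the protocol.

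**Formulas**

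- Analysed CD patients on biologics: n = N × 0.40 × 0.40 × 0.90
- Normal-approximation half-width: h = 1.96 × √(p(1 − p)/n)

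**Step 1. Reproduce the SAP figure (N = 3000).** 3000 × 0.40 × 0.40 = 480, and 480 × 0.90 = 432. At p = 0.5, h = 1.96 × √(0.25/432) = 4.71%, or 45.3% to 54.7%. This is the SAP's ±4.7% and the 3000 row of Table 2.

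**Step 2. Reproduce the protocol figure (N = 2000).** 2000 × 0.40 × 0.40 = 320, and 320 × 0.90 = 288. At p = 0.5, h = 1.96 × √(0.25/288) = 5.77%, or 44.2% to 55.8%. This is the protocol's ±5.8% and the 2000 row of Table 2. At p = 0.4 the half-width is 4.62% for 3000 and 5.66% for 2000. The same formula reproduces all seven rows of Table 2.

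**Step 3. Size of the gap.** 5.77 − 4.71 = 1.06 percentage points on each side, a ratio of √(3000/2000) = 1.22.

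**Step 4. Does the interval formula matter?** Both documents plan exact Clopper-Pearson intervals for binary data. With half the patients failing, 216/432 gives 45.2% to 54.8% (about ±4.8%) and 144/288 gives 44.1% to 55.9% (about ±5.9%). The gap is again about 1.1 points.

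**Step 5. Total needed for ±4.7%.** n = 1.96² × 0.25/0.047² ≈ 435 analysed, and 435/(0.16 × 0.90) ≈ 3020 enrolled, about half as many again as the protocol plans.

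**Step 6. Does the sentence about the other groups survive at 2000?** This step applies the 40/60 therapy split within both diseases and p = 0.5 to every group. The documents state the 40% to 50% failure rate only for biologics; p = 0.5 gives the widest interval.

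| Group | n at 3000 | h at 3000 | n at 2000 | h at 2000 |
|---|---|---|---|---|
| CD, biologics | 432 | 4.71% | 288 | 5.77% |
| CD, non-biological | 648 | 3.85% | 432 | 4.71% |
| UC, biologics | 648 | 3.85% | 432 | 4.71% |
| UC, non-biological | 972 | 3.14% | 648 | 3.85% |

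At 2000 the other three groups are still larger than the CD biologics group, so that sentence remains true.

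**The case against.** The strongest reply is that the right information is already available. Table 2, directly below the sentence, prints 288 patients and 44.2% to 55.8% for a total of 2000; footnote 2 discloses the reduction; and protocol section 15.4 has the correct paragraph. Neither document sets a precision threshold. Each calls its own figure acceptable, so ±4.7% is not a requirement that the study fails.

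Timing also reduces the weight. The SAP is dated 30.12.2021. Protocol section 10.2 planned the end of enrolment for Q2–Q3 2020, the last visit for Q2–Q3 2021, and the end of data collection for Q3–Q4 2021. On those dates the observed group sizes would be known or nearly so, and planned precision would have little further use.

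All of this stands, and it keeps the point minor. It does not remove the error: a final SAP names a superseded total as the justified one, and nothing in section 8.2 sends the reader to the 2000 row or to the footnote. A further fair point is that a final SAP should not be overwritten silently; the fix allows for that.

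**Conclusion.** The inconsistency is real and lies in current SAP text. Two figures in section 8.2, 3000 and ±4.7%, are out of date; the matching figures are 2000 and ±5.8%. For CD patients on biologics the planned interval is about 1.1 percentage points wider on each side than the SAP states, a relative increase of about 22%. This rests on the documents' own assumptions of 40% CD, 40% on biologics, 10% drop-out and a 50% failure rate, and it holds under the exact interval too.

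The severity is minor. No analysis, test or recruitment decision depends on the figure. The only change logged for v1.2 is the added subgroups, which is consistent with section 8.2 having been carried forward unrevised, though that is an inference.

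**What to change.** In SAP section 8.2, replace 3000 with 2000 and ±4.7% with ±5.8%, and refer to the 2000 row of Table 2 (288 patients, 44.2% to 55.8%). Leave Table 2 and the sentence on the other groups unchanged. Enter the correction in the SAP's history of changes, with a note that 3000 was the earlier planning basis. If data collection is already complete, protocol section 15 places later alterations in the study report, so record it there. Section 8.7 needs no correction, because footnote 2 already explains the 3000-case look.

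A related repair belongs in the protocol: section 10.2 lists interim analyses in 2019 and 2020, while section 15.3 says "One interim data analysis is planned in this study", in 2019. One line would reconcile them.

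The cost is two figures and a log entry in the SAP, and one line in the protocol. No patients are added and no analysis changes. The only downside is a slightly less favourable stated precision.
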